### **8.3 Questionnaires**

#### **St. George's Respiratory Questionnaire (SGRQ)**

The SGRQ is a disease-specific instrument designed to measure impact on overall health, daily life, and perceived well-being. It has been developed to be used by patients with fixed or reversible airway obstruction. It has been shown to correlate well with physiologic parameters and to show changes with time in patients with LAM (39). The administration is performed by face to face or telephone interview; completion takes approximately 10 minutes. The questionnaire consists of 76 items divided into 3 domains: symptoms (frequency and severity); activity (activities that cause or are limited by breathlessness); and impacts (social functioning, psychological disturbances resulting from airways disease).

#### **A Tool to Assess Quality of Life in LAM (ATAQ-LAM)**

ATAQ-LAM is a disease-specific instrument designed to assess health related quality of life in patients with LAM. The questionnaire consists of 32 items divided into 4 domains: exertional dyspnea, cough, fatigue, and emotional well-being.

#### **The EuroQOL visual analogue scale for quality of life**

The EuroQOL visual-analogue scale measures self-reported ratings of health status. Scores range from 0 to 100, with lower scores indicating worse functioning. Patients receiving sirolimus in the MILES trial had an increase in their scores on the EuroQOL scale as compared to the placebo group (12).

### **San Diego Shortness of Breath Questionnaire**

The San Diego shortness of breath questionnaire measures the quality of life impairment secondary to dyspnea resulting from pulmonary disorders. It is a 24-item measure that assesses self-reported shortness of breath while performing a variety of activities of daily living (40).

### **8.4 Biomarker Analyses**

VEGF-D biomarker analysis will be conducted on blood samples collected from each study patient at scheduled times. Assays will be performed by a central laboratory in Cincinnati. Serum VEGF-D has been shown to be elevated in patients with LAM and is a useful diagnostic, prognostic, as well as predictive biomarker (13, 14, 16).

### **8.5 Home Spirometry**

FEV1 and FVC will be obtained once weekly from patients agreeing to participate in the home spirometry sub study. Detailed instructions regarding the proper use of the home spirometer will be provided at the time of enrollment, along with access to detailed instruction manuals for future use. Once a week, patients will perform at least three spirometric measurements at approximately the same time, and record the best FEV1 and FVC values as their weekly results. These results, along with the associated flow-volume and volume-time loops will then be transmitted electronically to the study coordinator. The spirometric values as well as the loops will be reviewed in near real time along with direct feedback to the subject on the performance and trouble shooting of any issues by an expert pulmonary physiologist ([name] and/or [name]).

## 9. Risks

### 9.1 Risks of the investigational product

#### 9.1.1 Pharmacokinetics of resveratrol in humans

*Absorption:* In general, resveratrol is rapidly absorbed following oral administration. After oral administration, median time to achieve peak plasma concentration (Tmax) is approximately 30 minutes for low-dose resveratrol (41), and approximately 60-90 minutes for high-dose resveratrol (42, 43). Absorption of resveratrol is affected by food intake. Peak plasma concentration of resveratrol (Cmax) occurred 3 hours after a standard breakfast and 5 hours after consuming a high-fat meal (44). Co-administration of alcohol does not seem to affect resveratrol bioavailability (44).

*Distribution:* Because of its lipophilic nature, resveratrol has a high volume of distribution. Volumes of distribution ranging between 730 liters to 22000 liters have been described after ingesting resveratrol (44, 45).

*Metabolism:* Resveratrol undergoes extensive metabolism after human consumption. With small doses of resveratrol (up to 50mg per day), glucuronides are the main metabolites present in plasma (46). Monosulfates are the major metabolites when taking higher doses (> 250 mg per day) of resveratrol (47). It is possible that the resveratrol metabolites could act as a reserve for the parent molecule and, thus, contribute to resveratrol's pharmacological effects (48).

*Elimination:* The half-life of resveratrol varies depending upon the form of the drug. The half-life for micronized resveratrol is approximately 1 hour (49), whereas the half-life for nonmicronized resveratrol is approximately 8 hours (42). Resveratrol and its metabolites are mainly excreted through feces and urine (41). Fecal excretion is the major route of elimination for resveratrol and its metabolites accounting for greater than 70% of the excretion, with urinary elimination accounting for the remaining portions (41, 50).

#### 9.1.2 Safety Profile of Resveratrol in Humans

In general, resveratrol is a well-tolerated drug with a robust safety profile. No adverse effects related to resveratrol were reported in clinical studies evaluating doses up to 1 gram of resveratrol per day (50-55). Resveratrol is well tolerated even at higher doses, however there is an increase in the gastrointestinal side effects at doses exceeding 1 gram per day. Howells et al. conducted a phase I study evaluating the safety profile of a micronized oral formulation of resveratrol in patients with liver metastases of colorectal cancer. Six patients received 5 grams per day of resveratrol for a total of 14 days. Resveratrol was well tolerated, in general, with the most common adverse effects being mild nausea and diarrhea. Other adverse effects included chills, lethargy, rash, peripheral neuropathy, skin irritation and vascular flushing, which resolved without sequelae (49). Using the same dose and formulation in 24 patients with multiple myeloma, Popat et al. noticed a higher rate of development of adverse effects. The most commonly reported adverse events were: nausea (79%), diarrhea (71%), vomiting (54%), fatigue (46%) and anemia (38%). 54% of patients reported grade 3 adverse events; most commonly 21% hematological (anemia and thrombocytopenia), 21% renal failure, 13% nausea and 13% infections (56).

In a phase I study, 10 healthy volunteers were given 4 different strengths of resveratrol (0.5 grams, 1 gram, 2.5 grams and 5 grams per day). Resveratrol was well tolerated at all doses, with no serious adverse effect noted. Minor adverse events were seen in 57% of the patients, and were self-limited resolving 2-4 days post administration (45). The same study was repeated again yielding similar results. There were no serious adverse events related to resveratrol. However, subjects taking the higher dose of resveratrol (2.5 grams and 5 grams per day) had an increased incidence of gastrointestinal symptoms, including nausea, flatulence, abdominal discomfort and diarrhea. Most of these events were mild (severity grade 1, NCI CTCAE v.4.0), although 4 participants on the 2.5 gram and 5 gram doses presented with nausea and/or diarrhea of moderate severity (grade 2). The gastrointestinal side effects commenced after 2-4 days of the intervention and occurred half to one hour after resveratrol ingestion (42). Other studies have reported similar findings with an increase in the incidence of gastrointestinal side effects at resveratrol doses higher than 1 gram per day, with most side effects being mild and spontaneously resolving after a brief drug holiday (41, 44, 47, 57, 58). Due to the increased incidence of gastrointestinal side effects related to resveratrol at high doses (42), and the increased incidence of renal failure noted in one study (56), we have decided to limit the highest dose in our study at 1 gram per day.

Adverse reaction	Incidence (%)
Gastrointestinal disorders	
Nausea	10 - 15
Vomiting	8 - 12
Diarrhea	20 – 30
Flatulence	5 – 10
Abdominal discomfort	5 - 10
Nervous system disorders	
Headache	< 1
Peripheral neuropathy	< 1
General disorders	
Fatigue	< 5
Chills	< 1
Musculoskeletal disorders	
Myalgias and muscle cramps	< 1
Skin and subcutaneous tissue disorders	
Rash	< 1
Skin discoloration/irritation	< 1
Acne	< 1
Flushing	< 1
Hematologic disorders	
Anemia	2 - 4
Thrombocytopenia	2 - 4
Renal disorders	
Acute renal failure	0 – 4%
Laboratory abnormalities	
Elevated bilirubin	< 1

**Table 1:** Adverse reactions associated with the use of resveratrol (41, 42, 44, 45, 47, 49, 56-58). Percentages for the incidence of a particular adverse event are estimated after combining the patient numbers in clinical studies evaluating high dose resveratrol.

## 9.2 Risks of study procedures

**Questionnaires:** Participants will complete questionnaires about their health and basic information about demographics will be obtained. These procedures represent no more than minimal risk. Care will be taken to ensure confidentiality. Research records will be held in locked cabinets or locked storage rooms when staff members are not in attendance. All transmission of data to the investigators' laboratory for analysis will contain only subject's coded identification. Subjects' names or any other personal identifying information will not be used. Publication of results will involve aggregate data only so that individual participants cannot be identified. On occasion, it may be necessary, for legal reasons, or for good clinical practice, for third parties such as the IRB, to review medical records that are identified by name, but this should be an uncommon occurrence, and every effort will be made by the investigators to provide confidentiality.

**Blood draws:** The risks of blood draws include bleeding, bruising, discomfort, fainting and lightheadedness infection or pain at the needle site. All research personnel drawing blood are trained in the procedure and are familiar with proper infection control protocol.

**Pulmonary function tests:** In general, PFTs involve minimum risks, which will be reviewed with the subject prior to performing the testing. In general, these tests are well tolerated but occasionally some people may experience temporary tiredness, mild chest tightening, and coughing. Short acting bronchodilators such as albuterol will be available and will be administered if needed. Subjects with LAM are routinely evaluated with breathing tests as a matter of clinical care.

## 9.3 Adequacy of protection against risks

Each participant in this study will be informed of the intent of the study and asked to sign an IRB approved informed consent form. The consent form will fully describe the procedures, risks, alternatives, and potential benefits of the study. Consent will be obtained from eligible participants by a physician investigator or by the study research coordinator. The participants will be given the opportunity to refuse to participate in the study, under the assurance that such refusal will in no way affect their regular treatment. All questions asked by study subject will be answered to the best of the knowledge of the investigator and the study staff. Time will be given for the patient to read the consent form and ask questions prior to performing any study procedures. A copy of the signed and dated consent form will be given to subject prior to leaving the clinic. There are no alternatives in this study other than not to participate. Potential risks and benefits will be thoroughly explained to the subjects participating and they are free to withdraw from these studies at any point in time prior to or during the course of these investigations.

All information, data, etc., collected as a result of these studies is considered confidential and will be released only as required by law. Information published as a result of this study will be protected completely preserving the anonymity of the participants. Per HIPAA guidelines, research records will be stored in a locked room identified specifically as a patient record room. All transmitting of data is done by coded names and does not identify any types of names (first or last). Results of any procedures or tests will also be de-identified so as to hide the true identity of patient's names or any other identifiers. On occasion, it may be necessary, for legal reasons, or for good clinical practice, for third parties such as the IRB, FDA, or DSMB members to review medical records that are identified by name. This however would be on special occasions and would not be a common occurrence. Every effort in all areas of care will be made to keep the patient's information as confidential as possible. As noted above, we will minimize risks to human subjects by creating and maintaining a standard of excellence such as we had with our previous clinical trials in our sites. Such standard includes active interactions between faculty and staff on a weekly formal basis, and as needed otherwise, careful attention to training of staff in procedures and their possible complications, and a philosophy of 'patient first' in all of our dealings. Specifically, we use only trained personnel to perform procedures. The plan to handle adverse events is described in detail in the section of data and safety monitoring plan.

#### **9.4 Plans for assuring compliance with safety guidelines and regulations**

All clinical staff will be required to participate in training offered through their respective Institutional Review Boards. Training is also required in Health Insurance Portability and Accountability Act (HIPAA) in order to have access to study subject records. International Conference of Harmonization (ICH) Good Clinical Practice Guidelines (GCPs) are utilized daily in the clinical research practice and are reviewed periodically. The clinical research teams will have twice a month conference calls to provide an opportunity for staff to review and discuss the activities of the study. All clinical and laboratory staff are required to take courses handling blood borne pathogens on a yearly basis as well as training in laboratory safety, handling of biohazards, storage and shipping of clinical and laboratory specimens including dangerous goods.

## **10. Benefits**

### **10.1 Benefits of the investigational agent**

As with other studies investigating novel treatment for LAM, there may or may not be any benefits for the subject participating in the study. However, participation in this study will provide additional data on the safety and effectiveness of resveratrol for the treatment of LAM. Some participants in this study may benefit from the general evaluation of their disease from a qualified specialist for the duration of their participation in the trial. The participants may benefit from the physical exams, pulmonary function tests, and other study procedures. The information learned from this research study may benefit other subjects with LAM in the future. Subjects who participate in the study will receive all study medications at no charge, will have all testing at no cost to them or their insurance carrier (and the results of those tests will be made available to their primary care physician).

### **10.2 Importance of the knowledge to be gained**

In general, the knowledge gained from this study may benefit many subjects with LAM. The information obtained may improve the scientific community's understanding of the management of LAM. Specifically, the study will identify the safety and efficacy of the combination of resveratrol and sirolimus in LAM and thus may fundamentally alter the current clinical approach to patients with LAM.

[figure not shown]
### **10.3 Benefits of Study Procedures**

None.

## 11. Drug and Drug Procurement:

### 11.1 Resveratrol:

Resveratrol (3,5,4'-trihydroxystilbene) is a polyphenolic phytoalexin. It is a stilbenoid, a derivate of stilbene, and is produced in plants with the help of the enzyme stilbene synthase. It exists as two structural isomers: cis-(Z) and trans-(E). The molecular formula for resveratrol is C14H12O3 and its molecular weight is 228.24 g/mol. The structural formula of resveratrol is:

[figure not shown]

Resveratrol used in this study is manufactured by fermentation using genetically modified yeast in a process that results in *trans*-resveratrol with a purity of at least 98%. The product is free from DNA, proteins and cells from the production host. Resveratrol is available in the form of an off white powder that is highly lipophilic, and almost insoluble in water.

Resveratrol is available as white n°0 opaque capsules containing 125mg/capsule of resveratrol. The excipients present in the capsules are cellulose and magnesium stearate. Resveratrol capsules come in white plastic containers containing 200 capsules per container. Containers are to be stored at room temperature for a maximum of 2 years after encapsulation.

## 11.2 Sirolimus:

Sirolimus is an immunosuppressive agent. Sirolimus is a macrocyclic lactone produced by *Streptomyces hygroscopicus*. The chemical name of sirolimus (also known as rapamycin) is (3S,6R,7E,9R,10R,12R,14S,15E,17E,19E,21S,23S,26R,27R,34aS)-9,10,12,13,14,21,22,23,24,25,26,27,32,33,34,34a-hexadecahydro-9,27-dihydroxy-3-[(1R)-2-[(1S,3R,4R)-4-hydroxy-3-methoxycyclohexyl]-1-methylethyl]-10,21-dimethoxy-6,8,12,14,20,26-hexamethyl-23,27-epoxy-3H-pyrido[2,1-c][1,4]oxaazacycloheptenatriacontine-1,5,11,28,29 (4H,6H,31H)-pentone. Its molecular formula is C51H79NO13 and its molecular weight is 914.2. The structural formula of sirolimus is:

Sirolimus is a white to off-white powder and is insoluble in water, but freely soluble in benzyl alcohol, chloroform, acetone, and acetonitrile.

Sirolimus is available for administration as an oral solution containing 1 mg/mL sirolimus. Sirolimus is also available as a white, triangular-shaped tablet containing 1 mg sirolimus, and as a yellow to beige triangular-shaped tablet containing 2 mg sirolimus. The inactive ingredients in sirolimus Oral Solution are Phosal 50PG® (phosphatidylcholine, propylene glycol, mono- and di-glycerides, ethanol, soy fatty acids, and ascorbyl palmitate) and polysorbate 80. Rapamune Oral Solution contains 1.5% - 2.5% ethanol.

The inactive ingredients in sirolimus tablets include sucrose, lactose, polyethylene glycol 8000, calcium sulfate, microcrystalline cellulose, pharmaceutical glaze, talc, titanium dioxide, magnesium stearate, povidone, poloxamer 188, polyethylene glycol 20,000, glyceryl monooleate, carnauba wax, and other ingredients. The 2 mg dosage strength also contains iron oxide yellow 10 and iron oxide brown 70.

Patients will remain on sirolimus and continue to obtain those agents in the manner already established. Sirolimus has approval from the FDA for the treatment of LAM.

### **11.3 Accountability of Investigational Product**

Under Title 21 of the Code of Federal Regulations (21CFR §312.62) the investigator will maintain adequate records of the disposition of the investigational product(s)/intervention material(s), including the date and quantity of the drug received, to whom the drug was dispensed (participant-by-participant accounting), and a detailed accounting of any investigational product(s)/intervention material(s) accidentally or deliberately destroyed. Records for receipt, storage, use, and disposition will be maintained by the study site. A dispensing log will be kept current for each participant. This log will contain the identification of each participant and the date and quantity of investigational product(s)/intervention material(s) dispensed. All records regarding the disposition of the investigational product will be available for inspection by the DSMB, FDA, or IRB.

### **11.4 Assessment of compliance with the investigational product**

Drug adherence will be assessed by pill counts. Pill counts will not be done in the presence of participants to mitigate “dumping” behavior, and therefore allow more accurate assessment of drug use. Adherence will be reinforced using standardized non-judgmental questioning and tailored behavioral strategies.

## 12. Modification or discontinuation of the investigational product

### 12.1 Modification of investigational product

The product will not be modified during the course of the study by the investigator, pharmacy or subject.

### 12.2 Premature discontinuation of investigational product

Refer to sections 12.3 and 13.1.

### 12.3 Medication adjustments

#### 12.3.1 Dose Delays

For patients who are unable to tolerate the protocol-specified dosing schedule, dose adjustments are permitted in order to keep the patient on study drug. If administration of sirolimus must be interrupted because of unacceptable toxicity, drug dosing will be interrupted or modified according to rules described in Section 12.3.3. Sirolimus therapy may also be interrupted to accommodate surgical procedures or other invasive therapies at the discretion of treating clinicians. Major Events are non-treatment-related grade 3 and 4 pulmonary and non-pulmonary toxicities. Treatment should be delayed for major events if resveratrol may further complicate the non-treatment related event. If a major event requires a delay of treatment, treatment must be delayed until toxicity is resolved ( $\leq$  Grade 1 or  $\leq$  Baseline). For treatment-related toxicities and major events, if toxicity is not resolved in  $\leq$  4 weeks, patient will be taken off the treatment that is most likely to be related to the toxicity. While this most likely will result in withdrawal from study drug exposure at the investigator's discretion patients may continue on single agent therapy, if toxicities are  $\leq$  grade 2 and there is some evidence of clinical benefit to the patient.

Toxicity	Dose reduce first	Dose reduce second
Nausea	Resveratrol	Sirolimus
Diarrhea	Resveratrol	Sirolimus
Abdominal pain	Resveratrol	Sirolimus
Infections	Sirolimus	Resveratrol
Headache	Resveratrol	Sirolimus

**Table 2:** Approach to overlapping toxicities of sirolimus and resveratrol. The above table is a suggestion. Final decision on the order of dose reduction will be at the discretion of the investigator.

### 12.3.2 Resveratrol dose reduction

Any AE of  $\geq$  Grade 3 and attributed as possibly, probably or definitely related to resveratrol will result in the dose being held until the AE has resolved to  $\leq$  grade 1 or baseline, while sirolimus dosing may continue uninterrupted. If the AE resolves, reinstitution of treatment can occur but at a reduced dose as described in Table 3. If the AE recurs at the reduced dose, treatment will be held until the AE has resolved to  $\leq$  grade 1 and when resolved treatment can be reinstated at the next lower dose level. No more than 2 dose reductions are allowed during the maintenance cycles. Participants who are unable to tolerate the lowest dosage of resveratrol will be withdrawn from study drug exposure.

Toxicities that may be attributable to resveratrol include nausea, vomiting, abdominal pain, diarrhea, headache, and fatigue. If any of these AEs occur at grade  $\leq$  2, resveratrol may be continued and the AE managed with supportive care. For any AE with a grade  $\geq$  3, the rules outlined in Sections 14.2 – 14.10 apply for holding of dose, dose reduction, removal from study and reporting requirements.

Dose	Reduce to
250 mg daily	Hold or withdrawal from resveratrol exposure
500 mg daily	250 mg daily
1000 mg daily	500 mg daily

**Table 3:** Dose reduction schema for resveratrol

### 12.3.3 Sirolimus dose reduction

Known sirolimus toxicities will not be attributed to resveratrol but will only be attributed to sirolimus and may result in sirolimus dose modifications, at the discretion of the treating physician. Sirolimus trough levels will be checked at 2-, 4-, 8-, 12-, 16-, 18-, 20-, and 24- week intervals following study drug initiation. Sirolimus dose will be reduced if the serum trough level increases to a value greater than 10ng/ml. If sirolimus dose is reduced based on a high trough value, the trough level will be repeated 2 weeks after dose reduction. This process will be repeated until a sirolimus trough value less than 10ng/ml is achieved. The exact dose reduction scheme for sirolimus will be left at the discretion of the treating physician. Sirolimus toxicity monitoring labs will be performed as clinically indicated at the discretion of the physician. For severe/non-resolving toxicities, the treating physician may decide to stop sirolimus. Resveratrol may be continued as a single agent after sirolimus has been stopped. All reasonable efforts will be made to avoid sirolimus dose changes throughout the study duration, as long as it does not impact clinical patient care. A notification letter will be sent to the patient's primary pulmonologist about the patient's participation in the study and urging them to avoid sirolimus dose changes throughout the study duration, unless absolutely clinically indicated.

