#### **12.3.5 Prohibited medications**

Participants will not be allowed to receive any concomitant medication(s) that may interfere in the interpretation of data or the subject's participation in the study in the Investigator's opinion.

Metabolism of sirolimus occurs in the liver and the small intestine by the CYP3A4 family of enzymes. Thus, concomitant administration of sirolimus with other CYP3A substrates or inducers can alter the oral bioavailability of sirolimus (59). Although not a strong modulator of CYP activity, resveratrol has been reported to inhibit the activity of CYP3A4 *in vitro* and *in vivo* (60). Thus, co-administration of sirolimus and resveratrol has the potential to increase the blood levels of sirolimus or lead to an increase in the side effects of sirolimus. We will periodically monitor the sirolimus level during the study, as well as monitor closely for any adverse effects related to the study medications.

Because of the potential interaction with other drugs involving CYP3A4 metabolic pathways, strong inhibitors and strong inducers of CYP3A4 will not be allowed to be used concomitantly with the study medication. A washout period of 14 days will be required after discontinuation of the below listed medications before beginning the study medication. A list of the prohibited medications is provided in Table 4 below:

List of prohibited medications for this study
Strong CYP inducers
Barbiturates
Carbamazepine
Phenytoin
Rifampin, Rifabutin
St. John's Wort
Strong CYP inhibitors
Ketoconazole
Voriconazole
Itraconazole
Nefazodone
Clarithromycin
Erythromycin
Telithromycin
Gemfibrozil
Grapefruit juice

**Table 4:** List of prohibited medications for this study

Concomitant use of resveratrol with drugs with a narrow therapeutic range that are CYP3A, CYP1A2, CYP2D6, or CYP2C9 substrates (for example, theophylline,

tizanidine, warfarin, phenytoin, alfentanil, dihydroergotamine, ergotamine, fentanyl, pimozide, quinidine, cyclosporine, tacrolimus, thioridazine) will be prohibited from Day 1 until the end of study.

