## 14.7 Definition of Attribution

The attribution, of an adverse event to the study will be determined by the Principal Investigator or designated physician co/sub-investigator. The Principal Investigator or designee will record the determination of attribution on the appropriate adverse event or serious adverse event form. The attribution of an adverse event to the investigational drug or to a study procedure will be determined using the descriptors in the following table. For the purpose of this study, in addition to all study medications, the following procedures will be considered when determining attribution:

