## Attribution of adverse events

Code	Descriptor	Definition (guidelines)
UNRELATED CATEGORY		
1	Unrelated	The adverse event is clearly not related to study. The event is completely related to an etiology other than the study product or study intervention (the alternative etiology must be documented in the study subject's medical record)
2	Unlikely	The adverse event is doubtfully related to study and likely to be related to factors other than study product or study intervention.
RELATED CATEGORIES		
3	Possible	The adverse event may be related to study. There is an association between the event and the administration of study product and there is a plausible mechanism for the event to be related to the study product; there may be also an alternative etiology, such as characteristics of the subject's clinical status and/or underlying disease
4	Probable	The adverse event is likely related to study. There is (1) an association between the event and the administration of study product or study intervention, (2) a plausible mechanism for the event to be related to the study product, and (3) the event could not be reasonably explained by known characteristics of the subject's clinical status and or an alternative etiology is not apparent
5	Definite	The adverse event is clearly related to study. There is (1) an association between the event and the administration of the study product or study intervention, (2) a plausible mechanism for the event to be related to the related to the study product, and (3) causes other than the study product have been ruled out and/or the event re-appeared on re-exposure to the study product

(For additional information and a printable version of the NCI-CTCAE manual, consult the NCI-CTCAE website: <http://ctep.cancer.gov/reporting/ctc.html>) will be consulted.)

In a clinical trial, the study product\intervention will always be suspect when attributing an AE and the “unrelated” attribution will be used only when there is an undisputable or likely alternative explanation for the AE.

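### Section 12.3.3 bars attributing known sirolimus toxicities to resveratrol, which conflicts with 12.3.2 and partly with 14.7, so one event can receive opposite attributions

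*Combined protocol and SAP*

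**What the plan says.** Section 12.3.3, on sirolimus dose reduction, sets an attribution rule: "Known sirolimus toxicities will not be attributed to resveratrol but will only be attributed to sirolimus". The same sentence goes on to sirolimus dose changes at the treating physician's discretion. The term for the toxicities covered is not defined.

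Section 12.3.2, on resveratrol dose reduction, says: "Toxicities that may be attributable to resveratrol include nausea, vomiting, abdominal pain, diarrhea, headache, and fatigue". It also says that an AE of Grade 3 or higher "attributed as possibly, probably or definitely related to resveratrol will result in the dose being held". For AEs of Grade 3 or higher it adds that the rules in Sections 14.2 to 14.10 "apply for holding of dose, dose reduction, removal from study and reporting requirements".

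Section 14.7 has the Principal Investigator or a designee rate each event on a five-level scale. It says that "in addition to all study medications, the following procedures will be considered when determining attribution". The Possible level accepts that "there may be also an alternative etiology". The study product is to be suspected in every case, and the unrelated rating is reserved for events with an undisputed or likely other explanation.

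Three further passages bear on the question without setting an attribution rule. Table 2 in 12.3.1 is captioned "Approach to overlapping toxicities of sirolimus and resveratrol". Section 14.3.5 lists infections among the events expected for resveratrol. Section 12.3.5 says that giving the two drugs together "has the potential to increase the blood levels of sirolimus or lead to an increase in the side effects of sirolimus".

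**The concern.** The protocol gives investigators two incompatible instructions for events that both drugs can cause. One decides causality in advance for a whole undefined class of events; the other asks for a judgement on each event. Two raters who each follow the protocol could label the same event differently.

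Safety of the combination is the first secondary endpoint in section 4.2. Patients enter after at least 20 weeks of sirolimus, so when an event appears after resveratrol is added, the part played by the added drug is the open question. Section 5.6 gives the absence of prior human safety data on this combination in LAM as the reason for the dose-escalation design. A rule that settles the answer beforehand works against what the trial is meant to learn, and several participant-level rules depend on the label.

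**Working it through.** No figure in the plan is in dispute, so the check sets the passages side by side.

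**Step 1: which toxicities fall under both rules.** Section 12.3.3 gives no list, so I assume that the five toxicities in Table 2 count as known sirolimus toxicities, because the caption describes them as such. Abdominal discomfort in 14.3.5 is read as abdominal pain.

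| Toxicity in Table 2 | Named in 12.3.2 as possibly attributable to resveratrol | Listed in 14.3.5 as expected for resveratrol | 12.3.3 read literally |
|---|---|---|---|
| Nausea | yes | yes | sirolimus only |
| Diarrhea | yes | yes | sirolimus only |
| Abdominal pain | yes | yes | sirolimus only |
| Headache | yes | no | sirolimus only |
| Infections | no | yes | sirolimus only |

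Counts: 4 of 5 are in 12.3.2, 4 of 5 are in 14.3.5, and 5 of 5 are in at least one. The direct conflict is the four in 12.3.2. For infections the evidence is indirect, since an expected-event list is not an attribution rule. Vomiting and fatigue are in 12.3.2 but not in Table 2, so whether the bar reaches them depends on the undefined term.

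**Step 2: follow one event through both routes.** Take a Grade 3 diarrhea. Under 12.3.3 it is attributed to sirolimus only, so the condition for the hold in 12.3.2 is not met. Under 12.3.2 and 14.7 it can be rated Possible for resveratrol, so the condition is met. The referral of Grade 3 or higher AEs to Sections 14.2 to 14.10 includes 14.7, but 12.3.3 does not say that it yields, and the referral does not cover Grades 1 and 2.

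**Step 3: compare with 14.7.** A class-wide bar does not fit with always suspecting the study product, or with a Possible level that tolerates another cause. The conflict is partial, because 14.7 allows the unrelated rating where another explanation is likely. That exception is decided event by event, however, not for a class in advance.

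**Step 4: find the rules that depend on the label.**
- 12.3.2: the Grade 3 or higher resveratrol hold.
- 13.1.4: termination for recurrent or persistent toxicity related to resveratrol.
- 13.1.4: the treatment-failure label. It has two limbs. Withdrawal because the drug was not tolerated states no relatedness rating; only the limb on other untoward events related to the investigational drug depends on attribution.
- Section 15, Specific Aim #2: tables of events related to the drug, all grades. The drug is not defined. If it means resveratrol, the 12.3.3 label moves events out of the related count. If it means any study medication, as 14.7 suggests, a sirolimus label does not by itself do so.

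**Step 5: size.** No event rate is estimated. Section 9.1.2 reports no resveratrol-related effects at doses up to 1 g per day, and Table 1 combines high-dose studies, so neither gives a usable rate for this trial.

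**The case against.** The best defence is a narrower reading. Section 12.3.3 concerns sirolimus dosing and 12.3.1 deals with overlapping toxicities, so 12.3.3 could be meant only for toxicities peculiar to sirolimus. That is plausible, but the text does not say so, and the sentence states an attribution rule before it reaches dosing. The reading supports a clarification; it does not remove the need for one.

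It is also fair that Table 2 gives only a suggested order of dose reduction, that 14.3.5 lists expectedness, and that 12.3.5 describes a mechanism. A reader might infer that 12.3.3 contradicts all of these as well. It does not: they show that the blanket rule fits poorly, but none of them says how to attribute an event.

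A reader might further infer that resveratrol could not be held or reduced, or that events would be lost. The documents do not support that. Sections 5.5, 5.6 and 6.1 allow resveratrol to be held or reduced for side effects or intolerance. Section 12.3.1 provides for delay in some Grade 3 and 4 events unrelated to treatment, and 14.5 leaves removal from study agent to clinical judgement. None of these needs a formal rating. All AEs are recorded and tabulated regardless of cause, SAEs are reported regardless of relationship (14.3.4), and the DSMB reviews all AEs (14.1).

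Finally, a reader might infer that enrollment suspension or expedited FDA reporting would be switched off. That is not established. Section 13.1.3 refers to study drug or study medication, which may include sirolimus. Sections 7.2 and 14.8.1 and the suspected-reaction route in 14.8.2 also require an unexpected event. The opposite inference, that listed toxicities can never trigger them, fails too, because 14.3.6 lets a listed event be unexpected by severity or frequency.

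**Conclusion.** The inconsistency is real and should be fixed. Section 12.3.3 conflicts directly with 12.3.2 for four named toxicities and partly with 14.7 for events generally, and nothing says which governs. Followed literally, it can give the wrong causal label on the first-listed secondary endpoint. It can leave the 12.3.2 hold and the 13.1.4 resveratrol-related stopping rule untriggered when 12.3.2 and 14.7 would trigger them. It can also change the event-related limb of the treatment-failure label, although section 15 does not say how treatment failure enters the analysis. The effect on the related-event tables depends on the undefined term noted in Step 4.

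The conclusion rests on two assumptions: that the Table 2 toxicities are among the known sirolimus toxicities, and that 12.3.3 means what it literally says. What is at stake is the causal label and the rules tied to it, not the capture of events.

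**What to change.** Reconcile 12.3.3 with 12.3.2 and 14.7 so that one attribution rule applies to all grades, and state which passage governs. If any sirolimus-only rule is kept, list the toxicities it covers. In section 15, define which ratings, and for which drug, count as related to the drug in the tables. In 13.1.4, define relation to the investigational drug for the treatment-failure label.

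The cost is wording in 12.3.3, 13.1.4 and section 15, with no new visits or samples. Recording relatedness to resveratrol and to sirolimus separately, by extending the relationship item already collected under 14.4.2, is optional and costs one more rating per event. A separate rating for interaction is not required; it would be subjective, and a single-arm trial has no control group to check it against. No dose or clinical rule is proposed.
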